9.0 Regulatory and ethical compliance

This study was designed and shall be implemented and reported in accordance with the criteria of the “European Network Centres for Pharmacoepidemiology and Pharmacovigilance (ENCePP) study” and follows the ENCePP Code of Conduct (EMA 2014).

10.0 Data dissemination

Initial results will be presented in poster and/or oral format at appropriate thoracic conferences.

11.0 Advisory group

A steering committee has not been currently selected for this study.

13.0 Timelines

Table 8: Project timelines

Action	Timeline	Dates
Protocol development	3 weeks	(post phase 1 delivered Summer 2016)
Chiesi sign off	2 weeks	27 th October 2016
ADEPT application		27 th October 2016
OPC to obtain BLF Questionnaires	18 weeks	16 th May 2016
Data extraction	1 week	10 th November 2016
Cohort analysis	3 weeks	30 th November 2016
Initial/baseline report	3 weeks	24 th December 2016
Baseline Chiesi review	1 week	1 th January 2017
Sub-analysis	3 weeks	31 st January 2017
Final report writing (PowerPoint and Word report)	3 weeks	28 th February 2017
Chiesi review	1 week	10 th March 2017

15.0 APPENDIX

15.1 Appendix 1: Definitions

15.1.1 Body Mass Index (BMI)

The BMI is a representative measure of body weight based on the weight and height of the subject. It is defined as the weight (in kg) divided by the square of the height (in m) and is measured in kg/m². BMI will be categorised as follows: underweight (< 18.5), normal BMI (18.5 - 24.99), overweight (25-29.99), obese (≥30).

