4.3 Sub-analysis

- 1) To split the primary and secondary objectives by patients under 16 years of age and patients 16–65 years of age at the time of the index date.
- 2) To split the primary and secondary objectives by patients prescribed high dose (≥ 1000 μg of beclomethasone dipropionate and low dose < 1000 μg beclomethasone dipropionate).

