6.0 Study Population

6.1 Inclusion and exclusion criteria (questionnaire outcomes)

Inclusion criteria

Diagnosis for asthma (confirmed by diagnostic Read code)

Age ≤65 years at index date for main outcomes, all ages for exploratory

Two years of continuous practice data comprising 2-year data prior to questionnaire

Asthma questionnaire returned

Prescription of Aerochamber[®] or Volumatic[®] spacer prior to the questionnaire

≥2 separate prescriptions of non extrafine beclomethasone in the baseline year prior to the index date

Exclusion criteria

Received multiple types of ICS or FDC ICS/LABA during the baseline period or at the index date

Prescribed both Aerochamber and Volumatic spacers

Table 6: Inclusion and exclusion criteria for questionnaire outcomes

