7.1 Demographic and baseline variables for patient questionnaire outcomes

- Gender (male/female)

- Age of patient (years, at index date)
- Body Mass Index (BMI, at time nearest index date, calculated from height and weight data if available, otherwise taken from practice-recorded BMI value, detailed definition in Appendix 1)
- Smoking status (identified by Read code, closest to index date)
- SABA daily dose calculated 1 year prior to index date*
- Percentage predicted peak flow (closest to index date)
- Total cumulative ICS dose
- Spacer type
- Total cumulative non-extrafine beclomethasone dipropionate therapy
- Duration of ICS therapy
- Number of exacerbations (ATS/ERS 2015 consensus definition[†]) from 1 year prior to index date
- Number of oral corticosteroid prescriptions from 1 year prior to index date
- Number of antibiotic prescriptions for lower respiratory tract infections from 1 year prior to index date
- History of comorbidities related to asthma:
 - Pneumonia (Read code diagnosis from 1 year prior to the index date)
 - Diabetes (Read code diagnosis and/or antidiabetic drugs ever prior to the index date)
 - Ischaemic heart disease (Read code diagnosis before one year prior to the index date)
 - Rhinitis (Read code diagnosis, including chronic and allergic rhinitis and prescriptions for nasal steroids between one year prior to index date)
 - Eczema (Read code diagnosis between one year prior to index date)
 - Osteoporosis (Read code diagnosis between one year prior to the index date)
 - Charlson Comorbidity Index (based on Read code diagnoses between one year prior to index date, detailed definition in Appendix 1)

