8.3 Matching

Initially, baseline data will be compared between unmatched cohorts. Exact matching for categorical variables and coarsened exact matching for numeric variables will be used to match patients using 1:1 nearest neighbour matching, without replacement. Matching variables such as demographic data, disease co-morbidity and indicators of disease severity will be considered for selection using a combination of baseline data analysis and predictive modelling of the baseline data in relation to the primary outcome variable (independently of treatment group).

If patient numbers allow, patients will be matched on sub groups for age (under 16s and 16-65 year olds) and high/low average ICS dose (1000 µg non-extrafine beclomethasone dipropionate or more/under 1000 µg non-extrafine beclomethasone dipropionate). For the sub-question of step down patients, matching will be implemented if the numbers are sufficient.

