Oral corticosteroid prescriptions	N (% non-missing)	x (x)	x (x)	x (x)
	Mean (SD)	x (x)	x (x)	x (x)
	Median (IQR)	x (x, x)	x (x, x)	x (x, x)
Antibiotic prescriptions for LRTI	N (% non-missing)	x (x)	x (x)	x (x)
	Mean (SD)	x (x)	x (x)	x (x)
	Median (IQR)	x (x, x)	x (x, x)	x (x, x)
% Predicted Peak Flow	N (% non-missing)	x (x)	x (x)	x (x)
	Mean (SD)	x (x)	x (x)	x (x)
	Median (IQR)	x (x, x)	x (x, x)	x (x, x)

Table 29: Summary statistics for diagnoses of co-morbidities at baseline

		Volumatic®	Aerochamber®	p-value
Total (%)		x (x)	x (x)	x (x)
Pneumonia	N (% non-missing)	x (x)	x (x)	x (x)
	Mean (SD)	x (x)	x (x)	x (x)
	Median (IQR)	x (x, x)	x (x, x)	x (x, x)
Diabetes	N (% non-missing)	x (x)	x (x)	x (x)
	Mean (SD)	x (x)	x (x)	x (x)
	Median (IQR)	x (x, x)	x (x, x)	x (x, x)
Ischaemic heart disease	N (% non-missing)	x (x)	x (x)	x (x)
	Mean (SD)	x (x)	x (x)	x (x)
	Median (IQR)	x (x, x)	x (x, x)	x (x, x)
Rhinitis	N (% non-missing)	x (x)	x (x)	x (x)
	Mean (SD)	x (x)	x (x)	x (x)
	Median (IQR)	x (x, x)	x (x, x)	x (x, x)
Eczema	N (% non-missing)	x (x)	x (x)	x (x)
	Mean (SD)	x (x)	x (x)	x (x)
	Median (IQR)	x (x, x)	x (x, x)	x (x, x)
Osteoporosis	N (% non-missing)	x (x)	x (x)	x (x)
	Mean (SD)	x (x)	x (x)	x (x)
	Median (IQR)	x (x, x)	x (x, x)	x (x, x)
Charlson comorbidity index, n (%)	0	x (x)	x (x)	x (x)
	1-4	x (x)	x (x)	x (x)
	5+	x (x)	x (x)	x (x)

		Volumatic®	Aerochamber®	p-value
Total (%)		x (x)	x (x)	x (x)
Age (years)	N (% non-missing)	x (x)	x (x)	x (x)
	Mean (SD)	x (x)	x (x)	x (x)
	Median (IQR)	x (x, x)	x (x, x)	x (x, x)
Gender, n (%)	Male	x (x)	x (x)	x (x)
	Female	x (x)	x (x)	x (x)
BMI (kg/m ²)	N (% non-missing)	x (x)	x (x)	x (x)
	Mean (SD)	x (x)	x (x)	x (x)
	Median (IQR)	x (x, x)	x (x, x)	x (x, x)
BMI (categorised), n (%)	Underweight	x (x)	x (x)	x (x)
	Normal	x (x)	x (x)	x (x)
	Overweight	x (x)	x (x)	x (x)
	Obese	x (x)	x (x)	x (x)
Smoking status, n (%)	Current smoker	x (x)	x (x)	x (x)
	Ex-smoker	x (x)	x (x)	x (x)
	Mean (SD)	x (x)	x (x)	x (x)
	Median (IQR)	x (x, x)	x (x, x)	x (x, x)
Average SABA daily dose	N (% non-missing)	x (x)	x (x)	x (x)
	Mean (SD)	x (x)	x (x)	x (x)
	Median (IQR)	x (x, x)	x (x, x)	x (x, x)
Average SABA daily dose (categorised), n (%)	Low	x (x)	x (x)	x (x)
	Medium	x (x)	x (x)	x (x)
	High	x (x)	x (x)	x (x)
	Medium	x (x)	x (x)	x (x)
	High	x (x)	x (x)	x (x)
	Median (IQR)	x (x, x)	x (x, x)	x (x, x)
FEV ₁ /FVC ratio	N (% non-missing)	x (x)	x (x)	x (x)
	Mean (SD)	x (x)	x (x)	x (x)
	Median (IQR)	x (x, x)	x (x, x)	x (x, x)

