Exacerbation count	N (% non-missing)	x (x)	x (x)	x (x)
	Mean (SD)	x (x)	x (x)	x (x)

	Median (IQR)	x (x, x)	x (x, x)	x (x, x)
Oral corticosteroids prescriptions	N (% non-missing)	x (x)	x (x)	x (x)
	Mean (SD)	x (x)	x (x)	x (x)
	Median (IQR)	x (x, x)	x (x, x)	x (x, x)
Antibiotic prescriptions for LRTI	N (% non-missing)	x (x)	x (x)	x (x)
	Mean (SD)	x (x)	x (x)	x (x)
	Median (IQR)	x (x, x)	x (x, x)	x (x, x)
% Predicted Peak Flow	N (% non-missing)	x (x)	x (x)	x (x)
	Mean (SD)	x (x)	x (x)	x (x)
	Median (IQR)	x (x, x)	x (x, x)	x (x, x)

Table 30: Summary statistics for <16 age group

		Volumatic®	Aerochamber®	p-value
Total (%)		x (x)	x (x)	x (x)
Pneumonia	N (% non-missing)	x (x)	x (x)	x (x)
	Mean (SD)	x (x)	x (x)	x (x)
	Median (IQR)	x (x, x)	x (x, x)	x (x, x)
Diabetes	N (% non-missing)	x (x)	x (x)	x (x)
	Mean (SD)	x (x)	x (x)	x (x)
	Median (IQR)	x (x, x)	x (x, x)	x (x, x)
Ischaemic heart disease	N (% non-missing)	x (x)	x (x)	x (x)
	Mean (SD)	x (x)	x (x)	x (x)
	Median (IQR)	x (x, x)	x (x, x)	x (x, x)
Rhinitis	N (% non-missing)	x (x)	x (x)	x (x)
	Mean (SD)	x (x)	x (x)	x (x)
	Median (IQR)	x (x, x)	x (x, x)	x (x, x)
Eczema	N (% non-missing)	x (x)	x (x)	x (x)
	Mean (SD)	x (x)	x (x)	x (x)
	Median (IQR)	x (x, x)	x (x, x)	x (x, x)
Osteoporosis	N (% non-missing)	x (x)	x (x)	x (x)
	Mean (SD)	x (x)	x (x)	x (x)
	Median (IQR)	x (x, x)	x (x, x)	x (x, x)
Charlson comorbidity index, n (%)	0	x (x)	x (x)	x (x)
	1-4	x (x)	x (x)	x (x)
	5+	x (x)	x (x)	x (x)

Table 31: Summary statistics for comorbidities in <16 age group

		Volumatic®	Aerochamber®	p-value
Total (%)		x (x)	x (x)	x (x)
Age (years)	N (% non-missing)	x (x)	x (x)	x (x)
	Mean (SD)	x (x)	x (x)	x (x)
	Median (IQR)	x (x, x)	x (x, x)	x (x, x)
Gender, n (%)	Male	x (x)	x (x)	x (x)
	Female	x (x)	x (x)	x (x)
BMI (kg/m ²)	N (% non-missing)	x (x)	x (x)	x (x)
	Mean (SD)	x (x)	x (x)	x (x)
	Median (IQR)	x (x, x)	x (x, x)	x (x, x)
BMI (categorised), n (%)	Underweight	x (x)	x (x)	x (x)
	Normal	x (x)	x (x)	x (x)
	Overweight	x (x)	x (x)	x (x)
	Obese	x (x)	x (x)	x (x)
Smoking status, n (%)	Current smoker	x (x)	x (x)	x (x)
	Ex-smoker	x (x)	x (x)	x (x)
	Mean (SD)	x (x)	x (x)	x (x)
	Median (IQR)	x (x, x)	x (x, x)	x (x, x)
Average SABA daily dose	N (% non-missing)	x (x)	x (x)	x (x)
	Mean (SD)	x (x)	x (x)	x (x)
	Median (IQR)	x (x, x)	x (x, x)	x (x, x)
Average SABA daily dose (categorised), n (%)	Low	x (x)	x (x)	x (x)
	Medium	x (x)	x (x)	x (x)
	High	x (x)	x (x)	x (x)
	Medium	x (x)	x (x)	x (x)
	High	x (x)	x (x)	x (x)

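### One age-independent set of BMI bands is fixed for all patients, including the under-16 tables, and may misclassify many children

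*Protocol*

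**What the plan says.** The rule is in Protocol Section 15.1.1: "BMI will be categorised as follows: underweight (< 18.5), normal BMI (18.5 - 24.99), overweight (25-29.99", with obese from 30 kg/m² upwards. It is not limited to adults, and no centile or z-score is offered anywhere as an alternative.

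Both parts of the study rely on this definition. Section 7.1 (questionnaire part) has BMI calculated from height and weight, or "otherwise taken from practice-recorded BMI value, detailed definition in Appendix 1"; Section 7.2 (database part) says the same.

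Children are in the study by design. The age criterion in Sections 6.1 and 6.2 is "Age ≤65 years at index date for main outcomes, all ages for exploratory", so there is an upper limit but no lower one. Section 4.3 plans "To split the primary and secondary objectives by patients under 16 years of age and patients 16–65 years of age", and Sections 5.3 and 5.5 list under-16s as an age group to be characterised.

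The bands are carried into child-only output. The rows under "BMI (categorised), n" (%) are underweight, normal, overweight and obese. They stand in the table captioned "Summary statistics for <16 age group" (Table 30) and in the tables for under-16s on high dose (Table 38) and on low dose (Table 40). These are the caption numbers in Appendix 2; the list of tables in Section 2.0 numbers the same tables 28, 36 and 38.

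**The concern.** A fixed BMI threshold does not carry the same meaning at 4, 10 and 15 years, because BMI changes with age and differs by sex during growth. Bands without an age or sex qualifier can therefore err in both directions in children. A healthy child can fall under 18.5 and be called underweight, and a young child who is heavy for his or her age can sit between 18.5 and 24.99 and be called normal.

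The first thing at stake is whether the under-16 baseline tables can be read. They exist to show whether the two spacer groups are comparable among children. Categories that mostly reflect age would show little about weight status.

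The second is conditional. BMI is listed among the demographic and baseline variables, so it could be chosen for matching (Section 8.3) or as a covariate (Sections 8.4.1 and 8.4.2). If it entered as these bands in a pooled match of children and adults, the underweight class would put ordinary children together with truly underweight adults unless age was matched as well.

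This is not a detail left to a later analysis plan. The protocol states an explicit rule and applies it to child-only tables.

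**Working it through.** **Figure to reproduce.** None. The protocol gives no number for how children are distributed over the bands, and its sample-size statement has no bearing on this point.

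**Inputs from the Protocol.** Underweight cut-off 18.5 kg/m² and upper end of the normal band 24.99 kg/m² (Section 15.1.1); no lower age limit (Sections 6.1, 6.2).

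**Inputs assumed, not in the Protocol.** BMI in under-16s is taken as log-normal, with a median *m* of 15.5 to 20 kg/m² and a log-scale SD *s* of 0.10 to 0.15. The range of medians is wide because the age mix is not stated: low values stand for a mainly young group, high values for a mainly adolescent one.

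**Step 1. Share labelled underweight.** Share = Φ( ln(18.5 / *m*) / *s* ).

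Example, *m* = 15.5 and *s* = 0.10: ln(18.5/15.5) = 0.177; 0.177/0.10 = 1.77; Φ = 0.96.
Example, *m* = 20 and *s* = 0.10: ln(18.5/20) = −0.078; −0.078/0.10 = −0.78; Φ = 0.22.

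| Assumed median (kg/m²) | *s* = 0.10 | *s* = 0.15 |
|---|---|---|
| 15.5 | 96% | 88% |
| 16 | 93% | 83% |
| 17 | 80% | 71% |
| 18 | 61% | 57% |
| 18.5 | 50% | 50% |
| 19 | 39% | 43% |
| 20 | 22% | 30% |

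The full range is 22% to 96%. The share exceeds one half only when the median is below 18.5, and that holds for any continuous distribution, not just the log-normal. The figures count all children; they do not say how many of those labelled underweight are healthy.

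**Step 2. The other direction.** Take a child two log-SDs above the median, whose BMI is *m*·exp(2*s*).

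- *m* = 15.5: 15.5 × exp(0.20) = 18.9 and 15.5 × exp(0.30) = 20.9. Both fall in the normal band.
- *m* = 17: 17 × exp(0.20) = 20.8 and 17 × exp(0.30) = 22.9. Both fall in the normal band.
- *m* = 20: 20 × exp(0.20) = 24.4 (normal) and 20 × exp(0.30) = 27.0 (overweight).

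So under the lower assumed medians a child well above his or her peers is still labelled normal. The problem eases as the median rises.

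**Step 3. Where the bands are used.**

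- *Certain:* the BMI category rows of Tables 30, 38 and 40.
- *Possible:* Section 8.3 plans "Exact matching for categorical variables and coarsened exact matching for numeric variables" and picks the variables from demographic data, comorbidity and severity indicators. BMI is not named. If chosen, it could enter as a numeric variable or as bands; Section 8.2 also allows skewed variables to be categorised.
- *Possible:* Sections 8.4.1 and 8.4.2 adjust for baseline confounders that are not named.
- *Not used:* BMI category is not an outcome in Sections 7.3 to 7.5.

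**The case against.** The case for leaving the plan alone is that little depends on these rows. Continuous BMI (number, mean and SD, median and IQR) is tabulated directly above them. Both spacer groups are classified by the same rule. Age is a baseline variable in its own right, and Section 8.3 intends to match within under-16s and within ages 16 to 65 if numbers allow; where that is done, children are not paired with underweight adults. The non-inferiority endpoint is oral thrush or hoarseness, and no stated result has to change.

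All of this stands as a limit on the impact. It does not make the rule right for children. Continuous BMI that is not standardised has the same defect unless age is matched closely within childhood, and the matching by age subgroup is conditional.

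Three stronger readings are tempting, and the document supports none of them:

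- *Most healthy children would be labelled underweight.* That needs a median BMI below 18.5, and the protocol gives neither a BMI distribution nor an age mix. The Background cites guidance on spacers for under-5s and for ages 5 to 15, which makes young patients likely but does not give their share.
- *Matching or adjustment on BMI is already compromised.* BMI is not named for either, and nothing requires it to enter as bands.
- *The abnormal weight gain outcome is distorted.* In the questionnaire extracts (Figures 2 and 3) this is a yes/no box ticked by the patient or answered about the child. It is not derived from BMI.

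**Conclusion.** The point holds as a minor one. The protocol fixes one set of BMI bands without regard to age or sex and applies it to three under-16 baseline tables, so it may misclassify many children in both directions. The size is uncertain: 22% to 96% labelled underweight over assumed medians of 15.5 to 20 kg/m² and log-SDs of 0.10 to 0.15. Even at the top of that range of medians, 22% to 30% would be so labelled.

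The only certain consequence is that the BMI category rows in Tables 30, 38 and 40 cannot be read as weight status. An effect on matching or adjusted estimates depends on BMI being selected, and arises mainly if it enters as bands and children are not matched separately from adults.

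**What to change.** In Section 15.1.1, limit the four fixed bands to patients aged 16 and over. For patients under 16, define BMI as a centile or z-score standardised for age and sex against a named growth reference, with categories taken from that reference. Relabel the BMI rows of Tables 30, 38 and 40 to match, and use the same definition in any matching or adjustment that includes BMI. If children and adults are ever matched in one pool, make age group (under 16, 16 and over) an exact matching variable so that the two definitions do not meet within a pair.

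**Cost.** A short change to Appendix 1 and a reference lookup. Age, gender and BMI are already study variables, but Sections 7.1 and 7.2 list age at the index date and BMI from the time nearest to it. A growing child's BMI has to be standardised with age at the measurement, so the BMI measurement date must be extracted too. It is not listed among the variables at present.

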15.1.2 Asthma exacerbation (ATS/ERS consensus definition 2015)

Where an exacerbation is defined as an occurrence* of:

1. Asthma-related[†]: Unscheduled hospital admission / A&E attendance; OR
2. An acute[‡] course of oral steroids; OR
3. Antibiotics prescribed with lower respiratory consultation[§].

15.1.3 Comorbidities – Charlson Comorbidity Index (CCI)

The CCI was developed in the US in 1987 as a method of classifying prognostic comorbidity in longitudinal studies.¹⁵ It predicts the one-year mortality for a patient who may have a range of comorbid conditions such as heart disease, AIDS or cancer. Each condition is assigned a “weight” depending on the risk of dying associated with the condition; scores are then summed to give a total score predicting mortality.

*Where ≥1 oral steroid course / hospitalisation / antibiotics prescription occur within 2 weeks of each other, these events will be considered to be the result of the same exacerbation (and will only be counted once).

[†]**Asthma-related Hospitalisations:** consist of either a definite Asthma Emergency Attendance or a definite COPD Hospital Admission; OR a generic hospitalisation read code which has been recorded on the same day as a **Lower Respiratory Consultation**^{§§} (see below; (a) – (c) only and excluding where the only lower respiratory code recorded on that day was for a lung function test).

[‡] Acute oral steroid use associated with asthma exacerbation treatment will be defined as:

- all courses that are definitely not maintenance therapy, and/or
- all courses where dosing instructions suggest exacerbation treatment (e.g. 6,5,4,3,2,1 reducing, or 30mg as directed), and/or
- all courses with no dosing instructions, but unlikely to be maintenance therapy due to prescription strength or frequency of prescriptions.

where “maintenance therapy” is defined as: daily dosing instructions of ≤10mg Prednisolone or prescriptions for 1mg or 2.5mg Prednisolone tablets where daily dosing instructions are not available.

[§] **Lower Respiratory Consultations** - consist of the following:

- a) Lower Respiratory read codes (including Asthma, COPD and LRTI read codes);
- b) Asthma/COPD review codes excl. any monitoring letter codes;
- c) Lung function and/or asthma monitoring
- d) Any additional respiratory examinations, referrals, chest x-rays, or events.

The weights were revised and updated (for example, mortality due to HIV has fallen) by [name] (DFI) in their HSMR Methodology documentation¹⁶ and calibrated using UK data (due to differences in coding practice and hospital patient population characteristics from the US), using ICD-10 codes. As a result:

- DFI have expanded the coding definition of some conditions;
- Only secondary diagnoses (DIAG02-DIAG14) are now considered;
- There is greater variation in weights between conditions and the Charlson Index (the sum of the weights) can be treated as a continuous variable (limited to the range 0-50) for the purposes of risk adjustment.

The weights, codes and conditions used in this study are summarised in the table below.

Table 9: Co-morbid conditions and scores used in the Charlson Co-morbidity Index (CCI)

Condition	Condition name	ICD-10 codes	Weight
1	Acute myocardial infarction	I21, I22, I23, I252, I258	5
2	Cerebral vascular accident	G450, G451, G452, G454, G458, G459, G46, I60-I69	11
3	Congestive heart failure	I50	13
4	Connective tissue disorder	M05, M060, M063, M069, M32, M332, M34, M353	4
5	Dementia	F00, F01, F02, F03, F051	14
6	Diabetes	E101, E105, E106, E108, E109, E111, E115, E116, E118, E119, E131, E131, E136, E138, E139, E141, E145, E146, E148, E149	3
7	Liver disease	K702, K703, K717, K73, K74	8
8	Peptic ulcer	K25, K26, K27, K28	9
9	Peripheral vascular disease	I71, I739, I790, R02, Z958, Z959	6
10	Pulmonary disease	J40-J47, J60-J67	4
11	Cancer	C00-C76, C80-C97	8
12	Diabetes complications	E102, E103, E104, E107, E112, E113, E114, E117, E132, E133, E134, E137, E142, E143, E144, E147	-1
13	Paraplegia	G041, G81, G820, G821, G822	1
14	Renal disease	I12, I13, N01, N03, N052-N056, N072-N074, N18, N19, N25	10
15	Metastatic cancer	C77, C78, C79	14
16	Severe liver disease	K721, K729, K766, K767	18
17	HIV	B20, B21, B22, B23, B24	2

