7.5 Step down outcomes

- 1) Number of severe exacerbations in baseline year
- 2) Daily average SABA category in baseline year

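### The footnote defining an asthma-related hospitalisation lists a COPD admission and no asthma admission, so the exacerbation count can be misclassified to an unknown extent

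*Protocol*

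**What the plan says.** Section 15.1.2 of the Protocol defines an exacerbation by any one of three criteria. The first, qualified as asthma-related, is "Unscheduled hospital admission / A&E attendance; OR". The second is an acute course of oral steroids. The third is "Antibiotics prescribed with lower respiratory consultation". Qualifying events within two weeks of each other count once.

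The qualifier in the first criterion carries a footnote, printed on the page with section 15.1.3 and headed as the definition of asthma-related hospitalisations. It says these "consist of either a definite Asthma Emergency Attendance or a definite COPD Hospital Admission", and then adds a further route: "OR a generic hospitalisation read code which has been recorded on the same day as a" lower respiratory consultation. A companion footnote defines those consultations. Its item (a) is "Lower Respiratory read codes (including Asthma, COPD and LRTI read codes"), and its item (b) covers both asthma and COPD review codes.

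The definition is used in these places:
- Sections 7.1 and 7.2 list the exacerbation count as a baseline variable in both cohorts and refer the reader to Appendix 1.
- Section 7.5 gives "Number of severe exacerbations in baseline year" as the first of two step-down outcomes.
- Sections 4.2.3 and 8.4.2 describe the same comparison in terms of the exacerbation rate.

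**The concern.** The footnote's two named events do not belong to the same disease. The attendance term names asthma and the admission term names COPD. The study population is patients with asthma, the criterion is labelled asthma-related, and so is the footnote. The wording may have been carried over from a COPD definition, but the Protocol does not say so. An analyst working from it must either follow the rule as printed or change it without a documented basis.

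Two errors would follow from coding the text as it stands. A specifically coded asthma admission could go uncounted, and a COPD admission would enter as an asthma exacerbation. The count is a description of disease severity in both cohorts. In the exploratory step-down question it is itself an outcome compared between spacers.

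**Working it through.** No figure in the Protocol attaches to this definition, and the sample size in section 8.1 does not depend on it. The check is therefore a comparison of texts.

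**Step 1. Can COPD admissions occur in the cohorts?** Sections 6.1 and 6.2 require an asthma diagnostic Read code. Their exclusions concern multiple ICS types or fixed-dose ICS/LABA, and prescription of both spacers. COPD is not excluded, so patients with both diagnoses are eligible.

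**Step 2. Which records are counted?** Each row is what the record holds for one episode, within the two-week window.

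| Record for the episode | Criterion 1 as worded in 15.1.2 | Criterion 1 through the footnote | Counted as an exacerbation by any route |
|---|---|---|---|
| Coded asthma admission alone | Yes | No | No: missed |
| Coded asthma admission and definite asthma emergency attendance | Yes | Yes | Yes |
| Coded asthma admission and generic hospitalisation code on the day of a lower respiratory consultation (items a to c) | Yes | Yes | Yes |
| Coded asthma admission and acute oral steroids | Yes | No | Yes, by criterion 2 |
| Coded asthma admission and antibiotics with a lower respiratory consultation | Yes | No | Yes, by criterion 3 |
| Definite COPD admission alone | No | Yes | Yes: false count |
| Definite COPD admission and acute oral steroids | No | Yes | Yes, and criterion 2 would count it anyway |
| Generic hospitalisation code on the day of a COPD Read code | Not asthma-related on its face | Yes | Yes, through item (a) |

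The first and sixth rows are the direct result of the wrong term. In the second to fifth rows the asthma episode still counts once. The last two rows show COPD-related events entering by routes that a change to that one term would not close.

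**Step 3. What is the error per patient?** Let M be the number of asthma admissions in the first row and F the number of COPD admissions in the sixth row, after two-week merging. Counted minus intended exacerbations is then F − M. The Protocol gives no rate of asthma or COPD admission, and no information on how often the other routes are recorded. Neither M nor F can be estimated.

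**Step 4. Where does the count go?**
- Baseline description: directly, in both cohorts (7.1, 7.2 and the baseline mock tables).
- Step-down comparison: directly (4.2.3, 7.5, 8.4.2). Section 7.5 says severe exacerbations, for which Appendix 1 gives no separate definition, so the definition examined here is the only one available.
- Matching and adjustment: possibly. Section 8.3 says only that indicators of disease severity will be considered, and 8.4 refers to potential baseline confounders. Neither names the exacerbation count.
- Primary outcome (oral thrush or hoarseness) and secondary outcome (Read-coded adverse events): not defined by exacerbations, so affected only through matching or adjustment.

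**The case against.** The strongest reply is that this is a drafting slip with little consequence. The three criteria are alternatives, and an asthma admission will often come with an emergency attendance, a generic hospitalisation code, steroids or antibiotics. The main analyses stop at age 65 and include children, so COPD admissions may be few. The same rule applies to both spacer groups, and the Protocol gives no reason for misclassification to differ between them. The only direct comparative use is exploratory.

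Most of this stands as a limit on size. How often the other routes are recorded, and how few COPD admissions there are, remain assumptions that the Protocol does not support with figures. The reply does not remove the contradiction. Section 7.0 sends the reader to the appendices for variable definitions, so the Protocol has fixed this rule itself and has fixed it wrongly.

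Three stronger readings are tempting and are not supported:
- A reader might infer that the most severe asthma events are missed as a class. They are not; only admissions with no other qualifying record are lost.
- A reader might infer that matching rests on a faulty variable. The count is a candidate for selection, not a named matching variable.
- A reader might infer that changing the one term would take COPD out of the count. It would not, because COPD codes also enter through consultation items (a) and (b), and the steroid criterion as worded in 15.1.2 carries no asthma code of its own.

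**Conclusion.** The point holds as a wrong operational rule of unknown and possibly small effect. The footnote contradicts section 15.1.2 and its own heading. Followed literally, it can drop a specifically coded asthma admission that has no accompanying qualifying event, and it counts COPD admissions as asthma exacerbations. This bears directly on the baseline exacerbation count and on one of the two step-down outcomes.

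The Protocol does not support a claim that the non-inferiority result on oral thrush or hoarseness is biased. That would require the count to be chosen for matching or adjustment, and its misclassification to be large enough to leave material confounding. Neither can be established from the text.

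The conclusion rests on two assumptions: that extraction follows the footnote as printed, and that specific asthma and COPD admission codes occur in the data. It should be corrected because the rule is plainly inconsistent and cheap to repair, not because a large effect has been shown.

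**What to change.** Reconcile the footnote with section 15.1.2. In the data definition and the code list behind it, replace the definite COPD hospital admission with a definite asthma hospital admission.

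In the same edit, state whether the COPD Read codes and COPD review codes in lower respiratory consultation items (a) and (b) are meant to count towards an asthma exacerbation, since they feed both the generic-hospitalisation route and the antibiotic criterion. Also say whether the severe exacerbations in section 7.5 are those defined in Appendix 1 or a subset.

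The cost is one phrase, one or two clarifying sentences and a check of the code list; the list is not shown in the Protocol, so the work on it is assumed to be small. The Protocol is dated 28 October 2016 and section 13.0 dates data extraction 10 November 2016, 13 days later. The change belongs before that step; otherwise a correction made in programming would be an undocumented departure from the Protocol.
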